#### 3.8.2. SAMPLE SIZE CALCULATION

Current recommendations for external validation sample size calculation uses 3 criteria (outlined below) [37]. We based the observed events/expected events (O/E) on the outcome prevalence (20%), the calibration slope (assuming model is well calibrated, intercept=0, slope=1), and on the c-statistic (15% of the max Nagelkerke's R-squared).[37-39]. We have assumed the linear predictor is normally distributed with a common variance in event and non-event groups, prior to model development. Given this strong assumption, we will update these calculations after model development is completed.

1. O/E calculation

We assume O/E is 1 in the external validation population, with a 95% confidence interval width of 0.2 for O/E. he estimated sample size to satisfy criterion 1 is 1538 patients (~308 events).

2. Calibration slope

We assume model is well calibrated with intercept=0 and slope=1. We also assume the linear predictor distribution is normally distributed. For a 95% confidence interval width of 0.2, we would need a sample size of 4248 patients (~850 events).

3. C-statistic

Based on 15% of R^2 (i.e., max 15% Cox-Snell R2 of ~0.09 based on assumed prevalence),

which equates to a C-statistic of ~0.72. Using this estimated C-statistic value with targeted a SE(C) of 0.025, correspond to a confidence interval of width 0.1 (i.e., 0.67-0.77), we would need a sample size of 619 patients (about 124 events). Varying the expected C-statistic from 0.67 to 0.77 and based on the assumption above, a sample size of 531 patients (106 events) to 691 patients (138 events) would be needed, respectively.

Therefore, a minimum sample size of 4248 patients with 850 (20% of 4248) events would be needed for external validation to satisfy all three criteria.

Both regression models and machine learning approaches will then be externally validated on prospective data from one US hospital (Brigham and Women's Hospital), prospectively collected data from UK NHS Trusts and one UK clinical trial (Tight K study). In brief, for each individual in these datasets, outcome predictions will be calculated using the model developed with the Massachusetts General Hospital dataset and compared with the observed outcomes. The performance of the prediction models will be characterised by evaluating calibration and discrimination. To account for potential differences in case-mix (distribution of patient characteristics and prevalence of the outcome) between the US data (Massachusetts General Hospital dataset) used to develop the model and the prospective external validation, we will investigate whether recalibration is needed to update the model to better fit the UK population [35].

Heterogeneity in model performance will be explored over different hospitals using internal-external cross-validation [40, 41].

Finally, we will compare our prediction models to those existing prediction models identified from the systematic review where sufficient details are available from the original publication and predictors are available in the US data set.

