7.2.1 Databases

- 1. **CALIBER**: The Health Data Research UK CALIBER research platform contains variables extracted from linked electronic health records from primary care, hospital records, social deprivation information and cause-specific mortality data in England. This dataset includes electronic health records from 6.5 million individuals between 1998 and 2016.
- PRD: The Partners Research Database (PRD) contains detailed modern data for over 30,000 individuals undergoing cardiac surgery from 2 centres in the US between 2001-2020. PRD includes pre-operative echocardiographic measurements.
 Note: During the study, we will expand this database to include pre-and peri-operative variables from the clinical data warehouses of the two centres. It will be used for model development.
- 3. **Brigham**: The Brigham and Women's CABG Genomics Database is a prospective single centre detailed research database comprising 3000 individuals from 2001-2016. This dataset contains over 1,700 prospectively collected and curated pre, intra, and post-operative variables. It will be used for external US retrospective model validation.
- 4. **NHS Trusts**: The study will prospectively collect data from the UK NHS Trusts which will allow us to undertake external validation of PARADISE-1/PARADISE-2 with a total of approximately 6000 patients (2000 AFACS events) per annum. The NHS Trusts where data will be extracted from are:
 - a. Liverpool Heart & Chest NHS Foundation Trust
 - b. Barts Heart Centre (Barts Health NHS Trust)
 - c. Oxford University Hospitals NHS Foundation Trust

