### 2.2. OBJECTIVES

To develop and internally validate two prognostic models to predict postoperative atrial fibrillation after cardiac surgery using data available in the pre-operative assessment clinic or at admission for surgery (PARADISE-1); and data available on arrival in the postoperative care unit (PARADISE-2) from a single US centre (Massachusetts General Hospital).

To externally validate the developed models on three separate datasets: a US hospital (Brigham and Women's Hospital), a UK clinical trial (Tight K study) and prospectively collected data from UK NHS cardiac surgery centres.

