#### 3.3. MODEL DEVELOPMENT

The following procedures will be applied for the development of the two prognostic models. Information from all subjects in the Massachusetts General Hospital database will be used to develop the two predictive models proposed in this analysis plan. Both models will predict the same outcome (Atrial Fibrillation) after cardiac surgery but will differ in the predictors they use to predict the outcome.

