#### 3.3.1. Study setting and data collection

We will use the Massachusetts General Hospital (MGH) database to develop the PARADISE prediction models. The MGH dataset has two data sources:

- 1. the Research Patient Data Registry (RPDR): medical record data extracted from electronic hospital systems
- 2. the Society of Thoracic Surgeons (STS) Adult Cardiac Surgery Database: data gathered by trained extractors

Both data sources for the Mass General Hospital dataset will be used to develop our models and we will use retrospective pre-, intra-, and post-operative data for over 10,000 cardiac surgeries performed and recorded at this single US centre between 2003 and 2020.

It is important to note that some tables from this dataset were affected by a change in its electronic medical record system, which changed from Longitudinal Medical Record (LMR) to EPIC in April 2016.

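### SAP 3.8.2 plans hospital-level internal-external cross-validation although the models are developed in one hospital, leaving variation between NHS Trusts without a fixed-model analysis; its comparator filter also points to the wrong data

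*SAP*

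**What the plan says.** **Development.** Protocol 7.2.1 describes the development database (PRD) as covering patients "undergoing cardiac surgery from 2 centres in the US between 2001-2020". Protocol 11.2.1, under model development, then plans internal-external cross-validation over hospitals. The SAP narrows development to one hospital. SAP 3.3 states: "Information from all subjects in the Massachusetts General Hospital database will be used to develop the two predictive models", and SAP 3.3.1 describes surgeries "recorded at this single US centre between 2003 and 2020". SAP 2.2 agrees.

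**Validation.** SAP 3.8.1 names three validation data sets: Brigham, the NHS Trusts (three Trusts) and Tight K. SAP 3.8.2 says that for each patient in them "outcome predictions will be calculated using the model developed with the Massachusetts General Hospital dataset", and these predictions are set against the observed outcomes. The same text adds: "Heterogeneity in model performance will be explored over different hospitals using internal-external cross-validation". It does not say which hospitals enter or whether models are refitted.

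**Published comparators.** SAP 3.8.2 compares PARADISE with existing models "where sufficient details are available from the original publication and predictors are available in the US data set". Earlier in that text the US data are identified as "the US data (Massachusetts General Hospital dataset) used to develop the model". The protocol's primary objective includes the comparison, its primary outcome is performance in external data, and Protocol 7.5 describes the comparison under model validation with no such condition.

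**The concern.** Internal-external cross-validation fits the model on all hospitals but one, tests it on the one left out, and rotates. That suited a two-centre development set. The SAP changed the development set, and the sentence now stands in the external validation text with no hospitals named. Read against the development data it cannot be run. Read against pooled data it evaluates models other than the ones to be published.

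The practical loss is at Trust level. Nothing else in the SAP plans results for each Trust, so a single NHS estimate could conceal over-prediction in one Trust and under-prediction in another.

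The comparator sentence has a related fault. Having the predictors in the development data does not establish that a published model can be scored in Brigham, NHS or Tight K data. If the comparison were also run in MGH, it would favour PARADISE, which is fitted there.

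**Working it through.** **1. Feasibility.** With K development hospitals, each fold fits on K − 1.
- Protocol: K = 2, so 1 hospital to fit on.
- SAP: K = 1, so 0.
- Pooled over MGH, Brigham and three Trusts: K = 5, so 4. This is feasible, but every fold is a new model, whereas SAP 3.8.2 validates the MGH model as it stands.

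**2. Reproducing the SAP's precision figures** (SAP 3.8.2: 20% events, C about 0.72, CI width 0.2 for O/E and slope). SE = 0.2/(2 × 1.96) = 0.051.
- O/E: n = (1 − p)/(p × SE²) = 0.8/(0.2 × 0.051²) = 1,538. SAP: 1,538.
- Slope: n = V/SE², where V is the slope element of the inverse logistic information per patient. The linear predictor is normal with common variance in events and non-events, with variance (√2 × Φ⁻¹(C))². At C = 0.72, V = 11.49 and n = 4,417; at C = 0.725, V = 11.05 and n = 4,248. SAP: 4,248. The 4% gap is explained by rounding of C.

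**3. Can a pooled NHS estimate hide variation between Trusts?** Assumed for illustration only: 2,000 patients per Trust and true O/E of 0.85, 1.00 and 1.15. Trust CI = O/E × exp(±1.96 × √((1 − p·OE)/(n·p·OE))). Event rates: 20% (SAP 3.8.2) and 33% (2,000/6,000, SAP 3.8.1).

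| | 20% events | 33% events |
|---|---|---|
| Pooled NHS, n = 6,000, O/E 1.00 | 0.95–1.05 | 0.96–1.04 |
| Trust with O/E 0.85 | 0.77–0.94 | 0.79–0.91 |
| Trust with O/E 1.15 | 1.06–1.25 | 1.09–1.22 |

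The pooled figure looks well calibrated while two of the three Trusts exclude 1. The values were chosen to cancel, so this shows what is possible, not what is expected.

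**4. Precision of Trust-level results.** The documents give no split by Trust, so an equal split is assumed. They support two totals:
- About 6,000 NHS patients (Protocol 7.5 and 11.3): 2,000 per Trust.
- Synopsis prospective total of 13,684 less Tight K's 1,684 = 12,000: 4,000 per Trust.

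Slope half-width = 1.96 × √(V/n), with C = 0.72 and V = 11.49 (20% events) or 8.74 (33%).

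| Per Trust | 20% events | 33% events |
|---|---|---|
| 2,000 | ±0.149 | ±0.130 |
| 4,000 | ±0.105 | ±0.092 |

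The SAP's overall slope target is ±0.10. At 2,000 per Trust the C-statistic half-width (Newcombe formula) is ±0.028 or ±0.024, and O/E spans 0.92–1.09 or 0.94–1.06.

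**5. Comparator filter.** No arithmetic applies. The SAP's own gloss makes MGH the natural reading of the US data set. Protocol 12.3 uses a similar phrase for Brigham. Under neither reading does the condition test availability in the UK sets.

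**The case against.** The SAP moved the sentence from development to external validation and added a reference on large clustered data sets. That may be deliberate, with leave-one-hospital-out over MGH, Brigham and the Trusts in mind. Such an analysis is feasible and is described only as exploratory. This stands, so a reader who inferred that the analysis is impossible would go too far. It does not answer the point, because a pooled analysis refits the models, and the SAP neither names its hospitals nor says that it tests the strategy.

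A reader might also infer that heterogeneity between settings goes unexamined. The documents do not support that: Brigham, the NHS set and Tight K are each validated separately. The gap is confined to the Trusts.

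On comparators, a reader might infer that published models will be wrongly admitted or excluded, or that the comparison will be run in US data. The documents show neither. The condition governs eligibility only. The systematic review covers existing prediction models, and its variables feed the candidate list, with variables missing from the PRD to be taken from patient records (Protocol 7.3.1, 7.3.4; SAP 3.3.3). The panel-agreed list also governs UK extraction (Protocol 12.3). The panel may remove variables, but no affected model can be identified and the number may be small.

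Finally, it could be said that Trust-level estimates would be too imprecise. At 2,000 per Trust they fall short of the SAP's slope target. At 4,000 the shortfall nearly vanishes at 20% events and is gone at 33%.

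**Conclusion.** The point holds as an inconsistency in the SAP that should be corrected. As written, the hospital-level analysis either has no hospital left to fit on or reports refitted models. The fixed PARADISE models have no planned assessment in each NHS Trust. How much Trusts differ cannot be known from the documents, and the O/E illustration rests on invented values. The precision figures rest on an equal split, C of 0.72, 20–33% events and a calibrated linear predictor that is normal within events and non-events.

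The comparator filter is secondary. It applies the wrong eligibility test for a comparison that belongs in external data, and the number of models affected cannot be determined. Neither point affects the primary validation of PARADISE-1 and PARADISE-2 in the three data sets.

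**What to change.** 1. Replace the cross-validation sentence with calibration (O/E or intercept, and slope) and C-statistic of the unmodified MGH models, each with 95% CIs, in Brigham, each NHS Trust, and Tight K as one set. With about five units, any summary across them should be descriptive. If a pooled refit is kept, name its hospitals and label it a test of the modelling strategy.
2. Change the comparator condition to availability of predictors in the validation set used. State that the comparison is made in the external sets, on the same patients for all models.

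The cost is SAP wording and modest extra analysis, with no new data. Trust-level results will be less precise than the pooled NHS result, and some published models may drop out of some sets.

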5.2 Aim

The study aims to develop and validate two clinical prediction models to estimate the risk of a patient developing AF in the seven days following cardiac surgery, using data available:

- In the pre-operative assessment clinic or on admission for surgery (PARADISE-1)
- On arrival in the post-operative care unit (PARADISE-2)

Objectives	Outcome Measures	Timepoint(s) of evaluation of this outcome measure (if applicable)
Primary Objective To develop and externally validate two prognostic models to predict post-operative atrial fibrillation after cardiac surgery using data available in the pre-operative assessment clinic or on admission for surgery (PARADISE-1) and on arrival in the post-operative care unit (PARADISE-2); and compare their performance to other published models	 Primary outcome Discrimination (c-statistic) and calibration (intercept and slope) in external dataset Secondary outcomes Positive and negative predictive values, sensitivity and specificity 	7 days after cardiac surgery

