7.3.3 Expert panel – modified Delphi process

We will select a panel of international experts from relevant publications identified in our systematic review. The panel will undertake a modified Delphi process to identify a list of potential risk factors for AFACS.

Stage 1 of the Delphi process will involve panel members suggesting all risk factors they feel may be predictive of AFACS. These candidate variables will be collated and passed back to the panel in Stage 2. The panel will review all variables generated during stage 1, selecting those they judge to be most important. Variables meeting a consensus agreement of 60% will be accepted (56,57); those <20% will be rejected. In stage 3, variables with 20-60% agreement will be presented to the panel, along with their respective percentage agreement, for a final round of voting. Variables that achieve at least 60% agreement will be added to those previously accepted in Stage 2 to form the final list of candidate variables from the Delphi process.

7.3.4 Machine learning methods – exploring combinations of risk factors in CALIBER and PRD

We will combine all candidate variables identified from the systematic review, CALIBER analysis and Delphi into a combined "long-list". Any variables missing from the PRD (to be used for model development) will be extracted from the electronic patient record. We will then apply machine learning methods (see Section 10) to the CALIBER and PRD data sets to derive combinations of risk factors (i.e. interactions) that should be considered for inclusion in model development.

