7.3.5 Expert panel – consolidating risk factors to be used in model development

At their final meeting, the expert panel will review the final long-list of candidate variables (and their combinations). Any variables judged to be redundant or likely to represent spurious correlations will be removed.

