12.3 Data Recording and Record Keeping

All study records will be electronic – an overview of their generation is detailed above. All records will be subject to quality assurance polices both at the University and research group level. These are designed to guarantee the accuracy and validity of the study data.

The participants will be identified by a unique study number (pseudonymous study key).

We will use the CALIBER and PRD data sources to validate known (and potentially identify novel) risk factors for AF after cardiac surgery. A complete list of risk factors will not be known a priori, as it depends on the results of the systematic review and Delphi process. However, likely required data will be contained within following categories:

- Demographics (e.g., age, sex, ethnicity)
- Diagnostic coding (e.g., known chronic conditions)
- Limited pre- and post-operative medications (e.g., beta-blockers, vasoactive drugs)
- Limited surgical procedures and intraoperative findings (e.g., type of cardiac surgery, duration of bypass, blood transfusion)
- laboratory blood tests (including blood gases)
- vital signs (e.g., heart rate, blood pressure)
- Limited Echocardiogram findings
- Limited electrocardiogram (ECG) findings

Excluding age, sex and ethnicity we will not be accessing data on protected characteristics (e.g., religion, civil status, sexual orientation).

The expert panel will agree a final list of risk factors, which will be used to develop the two prediction models.

The models will be validated in one US data set (Brigham), one clinical trial data set (Tight-K) and prospective data collected from UK cardiac surgery centres (NHS Trusts). Only data from the above categories included in the candidate risk factor list agreed by the expert panel will be extracted from the UK cardiac centres along with the required outcome data for model assessment (including in-hospital

CONFIDENTIAL

mortality and episodes of atrial fibrillation). Tight-K is an ongoing clinical trial with its own approvals. Data for the NHS Trust data sets will be acquired from the individual Trusts patient records in collaboration with the respective organisations.

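### Does the SAP's reference to an unnamed US data set leave the comparison with published models open to bias?

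*SAP*

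**What the plan says.** The protocol's primary objective (table under 5.2) is to develop and externally validate the two models "and compare their performance to other published models". Its outcome measures, the c-statistic and the calibration intercept and slope, are to be obtained in external data. Protocol 7.5 and 11.2.2 repeat that the models will be compared with those found by the systematic review, without naming a data set. Protocol 7.5 mentions one comparator by name, CHA₂DS₂VASc.

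The SAP's objectives (2.2) do not list the comparison. It appears only at the end of SAP 3.8.2, where published models qualify "where sufficient details are available from the original publication and predictors are available in the US data set". Earlier in the same section the SAP speaks of case-mix differences "between the US data (Massachusetts General Hospital dataset) used to develop the model and the prospective external validation" and says of PARADISE that "we will investigate whether recalibration is needed to update the model to better fit the UK population".

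On predictors, Protocol 7.3.4 says "Any variables missing from the PRD (to be used for model development) will be extracted from the electronic patient record". Protocol 7.3.5 then has the expert panel review the list: "Any variables judged to be redundant or likely to represent spurious correlations will be removed". Protocol 12.3 says that only data "included in the candidate risk factor list agreed by the expert panel will be extracted from the UK cardiac centres", together with outcomes.

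**The concern.** The SAP has two US sources: MGH for development and Brigham for validation. Protocol 12.3 applies the term to Brigham: "The models will be validated in one US data set (Brigham), one clinical trial data set (Tight-K". The reader therefore has to infer which set is the screen for comparators and which set hosts the comparison.

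Three consequences would matter if the worst readings were right.

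- **Comparison in MGH.** PARADISE was fitted there and the published models were not. Bootstrap correction (SAP 3.5) removes overfitting, but not the advantage of sharing hospital, case mix and coding.
- **Comparison in Brigham alone.** With just over 2000 surgeries it meets the SAP's sizes for O/E (1538) and the c-statistic (619), but not for the calibration slope (4248).
- **Comparison in the NHS data.** A published model could pass a US screen and still not be computable, because the panel may have dropped one of its predictors before UK extraction.

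Recalibration is mentioned only for PARADISE. A comparator built to predict stroke gives no probability of AF after surgery, so a calibration comparison would need some mapping.

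**Working it through.** **Which US data set.** Within SAP 3.8.2 the US data are identified, in brackets, as the MGH dataset. The Brigham reading needs a phrase from a different document. MGH is the natural meaning, and the condition is then a practical screen on the data the analysts already hold.

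**Where the comparison is made.** The sentence stands in SAP 3.8, External validation, after text that lists three validation sets. Protocol 7.5, which holds the matching sentence, is headed Model validation. The primary outcome is defined in external data. All three point the same way, and no section plans a head-to-head in MGH or confines it to Brigham.

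**Whether the US condition does harm.** By plan, the UK extraction list is the long-list after the panel has trimmed it, and the long-list is what the US data are completed to hold. A comparator could therefore pass in the US and fail in the NHS set. The result would be no estimate for that model in that set, which readers would see; it is not a biased estimate. The final predictors are in the Case Report Form, which is not part of these documents, so no lost model can be shown.

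**Precision of the comparison.** Inputs:

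- c-statistic 0.72 (SAP 3.8.2) against 0.68, the best published figure in Protocol 5.1
- prevalence φ = 0.20 (SAP 3.8.2)
- NHS 6000, Brigham 2000 and Tight K 1684 patients (SAP 3.8.1)
- assumed, not in the documents: correlation r between the two estimates of 0.8 to 0.5

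SE(C)² = C(1−C)[1 + (n/2−1)(1−C)/(2−C) + (n/2−1)C/(1+C)] / [n²φ(1−φ)]

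This reproduces the SAP. The SE is 0.0255, an interval width of 0.10, at C = 0.72 with n = 619, at 0.67 with 691 and at 0.77 with 531. (The SAP prints the last two sizes in reverse order.)

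Half-width of the paired difference = 1.96 √(s₁² + s₂² − 2r s₁s₂)

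| Set | n | SE at 0.72 / 0.68 | r = 0.8 | r = 0.5 |
|---|---|---|---|---|
| NHS | 6000 | 0.0082 / 0.0086 | 0.0104 | 0.0164 |
| Brigham | 2000 | 0.0142 / 0.0148 | 0.0180 | 0.0285 |
| Tight K | 1684 | 0.0154 / 0.0162 | 0.0196 | 0.0310 |

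The difference between the inputs is 0.72 − 0.68 = 0.04, and every half-width in the table is smaller. The sets separate only against a gap of 0.02, which is 0.68 less the 0.66 for age alone in Protocol 5.1. At n = 2000, Brigham resolves 0.02 only for r above about 0.75. No document sets 0.02 as a margin.

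**Other sizes given in the documents.**

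- Brigham at the protocol's 3000 patients and about 900 events (30%): 0.0128 to 0.0203, so 0.02 is resolved for r above about 0.51.
- Protocol 7.5 expects one half to two thirds of trial recruitment to be usable. Applied to Tight K alone, that is 842 to 1123 patients. At 20% prevalence the half-width is 0.0241 (n = 1123, r = 0.8) to 0.0439 (n = 842, r = 0.5).
- The NHS figure of 6000 is per year in SAP 3.8.1. The synopsis total implies 13,684 − 1684 = 12,000, which gives 0.0074 to 0.0116.

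**Calibration slope.** Scaling the SAP's width of 0.2 at 4248 gives 0.2√(4248/6000) = 0.17 for the NHS set and 0.2√(4248/2000) = 0.29 for Brigham. The NHS set meets the SAP's target.

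**Recalibration.** An intercept shift or a positive slope update leaves the ranking of patients, and so the c-statistic, unchanged. The net-benefit analysis in SAP 3.7 covers the study's own regression and machine learning models; published models are not included.

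**The case for a change.** The strongest case for a change is that the comparison is part of the primary objective, that the SAP's own objectives omit it, and that one sentence is its whole specification. That sentence gives no data set, metric, pairing or rule for recalibrating comparators. With three validation sets, an analyst could in principle choose the most flattering one after seeing results, and naming the set would cost one line.

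The description of the text is accurate, and the US condition indeed does not test whether a model can be scored in UK data. The risk drawn from it is weaker. The protocol supplies the metrics. The ordinary reading of SAP 3.8 is that the comparison follows the validation through each set where a model can be computed. Reporting one set only would be visible beside the validation results for the other two. Scoring every model on the same patients and treating comparators alike in calibration are normal practice, and nothing in the plan contradicts them. The condition on published detail also screens out models without a usable equation wherever calibration is at issue.

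Tight K is the one place where precision could be poor: at half recruitment and r = 0.5 the half-width of 0.0439 exceeds 0.04. That comes from the size of the trial data set and would not be altered by wording in the SAP.

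**Conclusion.** The wording is loose, but the plan does not need to change. Read in place, the US data are MGH and the comparison belongs to the external sets. Neither a home advantage for PARADISE nor a comparison confined to Brigham is planned, and the size of any home advantage cannot be derived from the documents. A comparator that cannot be scored in the NHS data would be missing there, not misjudged.

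On the SAP's data set sizes the half-widths run from 0.0104 to 0.0310, all below the 0.04 gap between the planning value and the best published c-statistic. This rests on 20% prevalence in every set and an assumed correlation of 0.5 to 0.8; with reduced Tight K numbers it fails only towards the lower end of that correlation range. What remains is detail on pairing, recalibration of comparators and the list of sets, which a competent analyst would fill in without altering the conclusions.
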